Serious adverse events: A serious adverse event (SAE) is defined as one that poses a threat to the participant's life or functioning. We note that "severe" is not equivalent to "serious." A severe rash may not be a serious adverse event, whereas a heart attack of any severity is likely to be a serious adverse event. An SAE is defined as an event that entails one of the following:

- Death;
- Threat to the individual's life;
- Inpatient hospitalization or prolongation of existing hospitalization;
- Persistent or significant disability or incapacity;
- Intentional drug overdose;
- Any other significant event that jeopardizes the participant.

Routine reporting of AEs will be documented on the Adverse Event Log as described above. All AE data will be captured in the electronic database and reviewed by Drs. [name] and [name] every 6 months. AEs occurring at a greater than expected frequency or severity will be reviewed with the Steering Committee (Drs. [name], [name], [name], [name] and [name]). Investigators will provide this information to the Emory IRB according to IRB Policy & Procedures. The Steering Committee will decide if modifications to the protocol or consent form are required.

Reporting of Serious Adverse Events (SAE). If an adverse event meets the definition of an SAE, the PI in consultation with [name] (and Steering Committee if needed) will determine whether the SAE is possibly, probably or definitely related to the study intervention. The PI will report SAEs to the IRB and the funding agency within 10 days of the determination that the event meets one of these criteria: a) serious AND unanticipated AND possibly, probably or definitely related events; and b) anticipated adverse events occurring with a greater frequency than expected. Serious adverse events that do not meet any of these circumstances will be reported with IRB re-approvals.

Data Safety and Monitoring Plan

The study will be conducted in accordance with “good clinical practice” as outlined in the International Conference on Harmonization of Technical Requirements for Registration of Pharmaceuticals for Human Use (Dixon & Hallinan, 1999).

The study team will meet weekly and decisions will be made by consensus. The study team will provide oversight and ensure that the study is conducted in accordance with the protocol. The coordinator and the statistician have direct access to the PI if data quality or data safety issues emerge from reviews conducted by either the coordinator or the statistician.

The statistician will serve as an independent monitor of data quality and safety with input from study team. The statistician will have direct access to the data base to provide an additional check on missing data, attrition, adverse events and treatment response. As a single site study in a population that is well known to the clinical research team at Marcus, we do not see a need for an external Data and Safety Monitoring Board. The statistician will review the data set every six months. Questions and concerns will be brought to the study team and PI. To protect the blind, treatment assignment will not be divulged. The discussion with the study team is likely to focus on individual cases and overall trends. Given the sample size of 138(updated from 150), we have not declared any stopping rules for benefit or futility. In the highly unlikely occurrence that adverse events show group differences, the study team will seek advice from the Marcus Center Director, [name]. He is supportive of the study, but not directly involved.

References

Arnold, L. E., Vitiello, B., McDougle, C., [name], L., Shah, B., Gonzalez, N. M., Chuang, S., Davies, M., Hollway, J., Aman, M. G., Cronin, P., Koenig, K., Kohn, A. E., McMahon, D. J., & Tierney, E. (2003). Parent-Defined Target Symptoms Respond to Risperidone in RUPP Autism Study: Customer Approach to Clinical Trials. *Journal of the American Academy of Child and Adolescent Psychiatry*, 42(12), 1443-1450.

Blum, N. J., Taubman, B., & Nemeth, N. (2003). Relationship between age at initiation of toilet training and duration of training: A prospective study. *Pediatrics*, 111, 810-814.

Busner, J., & Targum, S.D. (2007). The clinical global impressions scale for severity. Washington DC: Psychiatric Measures.

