will be gathered to determine if problem behavior is likely to interfere with the treatment protocol. If problem behavior is deemed likely to interfere they will be excluded from participation. Caregivers will also be asked to keep a log of the frequency of their child's continent and incontinent bowel movements from the day of the phone screen until the characterization appointment to further confirm study eligibility.

Characterization, the Medical Assessment, and collection of Baseline Measures will take place across either 1 or 2 days, depending on participant and clinician availability, as well as the ability of the participant to tolerate lengthy assessments. Although the medical screening may precede characterization if scheduling requires, characterization will take place first whenever possible because participants are thought to be more likely to meet diagnostic exclusionary criteria than medical exclusionary criteria.

Consenting: A member of the research team will obtain informed consent from the caregiver(s) of each participant prior to completing any study procedures. We will not obtain assent from participants because it is anticipated that most will not possess the cognitive capacity to give assent and because refusal to comply with toileting routines is the condition that is being targeted for intervention. At this meeting caregivers will be asked to keep concomitant medications stable and to notify us if this is not the case during the study. Caregivers of participants will be provided a handout that addresses frequently asked questions about the use of suppositories.

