Group Assignment: Participants will be randomly assigned to one of the two groups after they have it has been verified that they meet all of the eligibility criteria. Randomization to 2-week MIE or TAU will be according to a 1:1 ratio using permuted blocks stratification on constipation status. The permuted blocks will be constructed and managed by the unblinded statistician. She will receive an email form from the coordinator indicating that the participant meets all inclusion criteria and does not meet any exclusion criteria and the participant's constipation status (constipated/not constipated). This statistician will assign the subject to 2-week MIE or TAU according to the permuted block. We define constipated using the modified Rome III criteria appearing above. All other participants will be considered not constipated. Caregivers of participants randomly assigned to the MIE condition (i.e., 2 week) will be provided a handout that addresses frequently asked questions about the use of suppositories.

In the event a participant is unable to attend MIE or TAU visit(s) in the clinic after being enrolled into their assigned group, the clinician and therapists have the option to administer the intervention or TAU consultation via telehealth with the participant (e.g., WebEx, Zoom). In order to utilize telehealth, a scenario must arise that prevents the participant from being able to complete the MIE treatment or TAU consultation in the clinic. If such a scenario arises, on a case-by-case basis, then the therapist and clinician may administer via telehealth, but should return to the clinic as soon as possible to continue. Additionally, there will be one extra day added to the MIE 2-week treatment totaling 11 days instead of 10. The extra day is added to the beginning of treatment so the clinician can first explain the intervention they will be doing with the caregiver.

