Baseline Phase (Weeks 1-2): All participants' caregivers, regardless of group assignment will implement any medical recommendations for constipation throughout a Baseline Phase. In addition, all caregivers will collect data on their child's bowel movements during Baseline. It is anticipated that this phase will last for 14 days, but due to scheduling issues it may last for 12 to 21 days. Data collection will include frequency of continent and incontinent bowel movements and whether any medication (i.e., a suppository) was used prior to the bowel movement on data sheets provided by the research team. Caregivers will be asked to enter data from the datasheets electronically directly into our project database via a unique and secure login provided during the characterization visit. Caregivers who do not enter data for a given day will receive a reminder email the next day. A research coordinator will also call caregivers who are missing data on a weekly basis to see if they entered it on the datasheet but did

not enter it electronically. In cases in which the family does not have access to the internet, the data will be collected over the phone. Caregivers will be asked to bring the data sheets to their first visit in the clinic.

Baseline Visit: Baseline data will be collected on the first day of MIE or TAU, before the appointment occurs. A member of the research team will meet with caregivers to complete the remaining baseline measures. The following measures will be completed: Parent Target Problem (PTP), Parenting Stress Index-Short Form (PSI-SF), Aberrant Behavior Checklist (ABC) Clinician Global Impression-Severity (CGI-S), Caregiver Strain Questionnaire-Short Form (CGSQ-SF), Adverse Event, Safety Review, Concomitant Medication Log .

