Reminder Calls: During the 18 Week Home Implementation Phase, the study team will make monthly, scripted phone calls to participants. These phone calls will serve to remind the parents to continue to implement the intervention procedures they were taught and to confirm that they have an adequate supply of study medication. These calls will be scripted and parents will not be given any additional insight or clinical guidance. If necessary, parents will be reminded that they are participating in a research study and that the goal is to determine the intervention's effectiveness up to their Week 28 Follow Up visit. Parents will also be reminded that they will receive clinical guidance after completion of their Week 28 visit. However, the study team may intervene clinically and terminate study participation if they feel the child is in need of immediate emergency medical treatment.

Visit Windows

The visit window between Characterization/Medical Assessment and Baseline/MIE Treatment or the TAU consultation visits is 12 – 21 days. MIE Treatment or the TAU consultation visit must occur after the Week 2 Baseline. During this time, parents must collect a minimum of 7 days of toileting home data. These days do not need be consecutive.

The Week 4 Midpoint visit will occur 7-21 days after the Week 2 Baseline Visit (2 weeks +/- 7 days). The Week 8 Endpoint visit will occur 35-49 days after the Week 2 Baseline Visit (6 weeks +/- 7 days). Week 28 Follow Up will occur 175-189 days after the Week 2 Baseline Visit (26 weeks +/- 7 days).

Study Measures

Characterization Measures:

Autism Diagnostic Observation Schedule (ADOS; Lord et al., 2000) The ADOS is an

investigator-based procedure that places the child in naturalistic social situations demanding specific social and communication reactions. The ADOS provides a sample of the child's behavior in a naturalistic setting. Behaviors are coded in the areas of social communication, social relatedness, play and imagination, and repetitive behaviors. The ADOS contributes to the DSM 5 diagnosis of ASD.

Autism Diagnostic Interview-Revised (ADI-R) (Rutter, LeCouteur, & Lord, 2003). The ADI-R is a structured interview that is used to diagnose autism. The interview can be administered to a caregiver and is composed of 93 items. The instrument includes the three functional domains related to ASD: Language and Communication, Reciprocal Social Interactions, and Restricted, Repetitive, and Stereotyped Behaviors and Interests.

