Secondary Outcome #2: ANCOVA will be used to compare change in parental stress and strain from baseline to Week 8 as measured on the Parenting Stress Index and the Caregiver Strain Questionnaire. The contrast will be MIE-2 vs TAU.

Sample Size and Power Calculation for Primary Outcomes. As noted above, we will perform one planned pairwise comparison for the primary outcomes at Week 8: MIE-2 vs TAU. We set our significance level for alpha as 0.05 to control the family-wise Type I error rate at the 5% level. Based on our pilot data, we conservatively estimate the following rates of children achieving continence at Week 8: 10% of participants in TAU, 75% of those in the MIE-2 group and 50% for the MIE-1 group. With a sample size of 54 in each of the TAU MIE groups, we can detect a 29% difference in response rate on our primary categorical measure with 15% dropout rate and type I error rate of 0.05. We propose that this will be a valid test of the Two-week medical-behavioral intervention, which was, and remains, the primary aim of the study.

Data Security

Electronic Protected Health Information (ePHI) is carefully guarded within the database. All full and incremental database backups are compressed and encrypted before being sent using secure sockets layer (SSL) to a secure, geo-redundant backup infrastructure. All communication with the server for normal usage, maintenance and backups is encrypted using SSL.

The DEX database has the following Security features:

Hot Security The server runs a highly secure operating system (FreeBSD), providing immediate resistance to many common attacks and exploits. A unique web-server is used to reduce system exposure to attacks. The web server is written in a high-level language that substantially reduces the effectiveness of most common attacks (such as buffer-overflows). All communication between the site server and remote workstations (any modern computer capable of running the Firefox web browser) is logged and uses SSL encryption. The system fully supports journaling to ensure data integrity, to support audit trails, and to simplify disaster recovery. Furthermore, all collected data, as well as the journal itself, can be mirrored (in encrypted form) on redundant remote servers. In the rare case that the server is compromised, any modification to system resources can be undone by simply contacting Prometheus Research, who will restore the system from backup.

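### The protocol gives two conflicting times for baseline PSI-SF and CGSQ-SF; on the later one, the Secondary Outcome #2 baseline is a post-randomisation self-report from unblinded caregivers

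*Combined protocol and SAP*

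**What the plan says.** All references are to the combined protocol and SAP.

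- **Procedures, Screening** (the paragraph before Consenting): "Characterization, the Medical Assessment, and collection of Baseline Measures will take place across either 1 or 2 days".
- **Procedures, Group Assignment**: participants are "randomly assigned to one of the two groups after they have it has been verified that they meet all of the eligibility criteria". The unblinded statistician assigns the arm on receipt of an eligibility email from the coordinator. No day is fixed.
- **Procedures, Baseline Phase**: "All participants' caregivers, regardless of group assignment will implement any medical recommendations for constipation throughout a Baseline Phase". The phase is expected to take 14 days, but "due to scheduling issues it may last for 12 to 21 days".
- **Procedures, Baseline Visit**: "Baseline data will be collected on the first day of MIE or TAU, before the appointment occurs". The visit is said to cover the remaining baseline measures, and the list then includes PTP, PSI-SF, ABC, CGI-S and CGSQ-SF.
- **Visit Windows**: "The visit window between Characterization/Medical Assessment and Baseline/MIE Treatment or the TAU consultation visits is 12 – 21 days".
- **Table 1.0** has a Baseline Measures column separate from Characterization & Medical Assessment, but does not place either relative to randomisation.
- **Analytic plan, Secondary Outcome #2**: "ANCOVA will be used to compare change in parental stress and strain from baseline to Week 8". The covariates are not named.
- **Blinding**: the independent evaluators are blind. Nothing describes blinding of caregivers, and nothing says when families are told their arm.

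**The concern.** A baseline covariate is safe in a randomised comparison because assignment cannot have affected it. That holds if PSI-SF and CGSQ-SF are completed with the eligibility assessments. It is not guaranteed if they are completed on the first treatment day, because the arm is already set by then.

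Both instruments are caregiver self-reports of stress and strain. A parent about to start two weeks of daily visits and a parent about to attend one consultation may answer differently, from relief, disappointment or expected burden. ANCOVA would treat such a gap as a chance imbalance and adjust for it, which carries a distortion into the Week 8 contrast. If MIE parents report more stress at baseline because of their assignment, the adjustment favours MIE. If they report less, it works against MIE.

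**Working it through.** **Timing, from the text**

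1. Assignment follows verified eligibility (Group Assignment).
2. The Baseline Phase is described as running with group assignment already in place (Baseline Phase).
3. The baseline questionnaires are taken on the first day of MIE or TAU (Baseline Visit). That day can be scheduled only once the arm is known to the study.
4. The 12 to 21 days run from Characterization/Medical Assessment (Visit Windows). The gap from randomisation to baseline is therefore at most about 21 days. It equals 12 to 21 days only if randomisation happens on the day of the eligibility visits, which is not stated.
5. The Screening sentence contradicts step 3. The reference to remaining measures under Baseline Visit does not resolve this, because both caregiver questionnaires are then listed for that visit.

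**Size, for illustration**

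The plan gives no figure for Secondary Outcome #2. The number evaluable comes from its sample-size paragraph: 54 per arm with 15% dropout gives 54 × 0.85 = 45.9, taken as 46.

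Assumptions not in the documents:
- equal SDs at baseline and Week 8;
- baseline to Week 8 correlation r;
- an arm-related shift of d SD in baseline reporting only, gone by Week 8;
- baseline as the ANCOVA covariate;
- a two-sided 5% test.

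Formulas, in SD units:
- size of bias = r × d
- SE = √[2(1 − r²)/46]
- type I error = P(|Z + bias/SE| > 1.96)

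At r = 0.6 and d = 0.2:
- bias = 0.6 × 0.2 = 0.12
- SE = √(2 × 0.64/46) = 0.167
- bias/SE = 0.72
- type I error = 11.1%

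Range:

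| d | Bias, r = 0.5 | Type I error, r = 0.5 | Bias, r = 0.7 | Type I error, r = 0.7 |
|---|---|---|---|---|
| 0.1 | 0.05 | 5.9% | 0.07 | 7.6% |
| 0.2 | 0.10 | 8.6% | 0.14 | 15.6% |
| 0.3 | 0.15 | 13.2% | 0.21 | 29.2% |

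A simulation of 4,000 trials per setting gave 5.0% to 29.2% over the same cells, and 5.3% to 5.4% with no shift.

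If change were compared with no baseline covariate, the bias would be the full d. At r = 0.6 and d = 0.2, SE = √[2(1 − 0.6)] × √(2/46) = 0.186 and type I error is about 19%.

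**If the shift persists to Week 8**

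With the same r, d and SE, and an equal shift at Week 8:
- first-treatment-day baseline: (1 − r)d = 0.4 × 0.2 = 0.08 SD, type I error about 8%
- pre-randomisation baseline: d = 0.20 SD, type I error about 22%

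**The case against.** **Arm knowledge is inferred.** No section says when families are told. Group Assignment says that "Caregivers of participants randomly assigned to the MIE condition (i.e., 2 week) will be provided a handout that addresses frequently asked questions", but the Consenting paragraph also promises caregivers of participants a suppository handout, so the handout does not show disclosure. This stands, and the wording should be that caregivers very likely know. The inference is still strong, because families must arrange either daily visits over two weeks or one appointment, and no delayed disclosure is described.

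**The defect is conditional.** If the Screening sentence governs, the baseline can precede assignment and the problem disappears. This also stands. What is certain is the conflict; the bias follows only from the later timing.

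**The illustration is one-sided.** No document supports any value of d. If the reporting shift lasts to Week 8, a first-treatment-day baseline absorbs part of it and an earlier baseline does not, as the last calculation shows. This is correct. A persisting shift is a problem of unblinded reporting, and it biases parent-reported outcomes whichever baseline is used. It is not a reason to prefer a covariate that assignment may have altered, but it does mean that the fix removes only one route of bias.

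**Stronger readings a reader might reach.**
- That baselines are taken 12 to 21 days after randomisation: the window is counted from the eligibility visits.
- That the CGI-I anchor is compromised in the same way: a blind evaluator writes the PTP narrative and rates it with all available information, so exposure is only through what the caregiver reports and approves. Most of it would remain at Week 8 whatever the baseline timing.
- That the primary result is at risk: its chi-square test uses Week 8 continence only.

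**Conclusion.** The point holds in limited form. The sections conflict on when baseline measures are taken. On the Group Assignment, Baseline Visit and Visit Windows text, the PSI-SF and CGSQ-SF baselines are post-randomisation self-reports from caregivers who are not blinded. The plan has no safeguard in the analysis.

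Only Secondary Outcome #2 is directly exposed. The 0.12 SD and 11% figures show what a modest shift could do under the stated assumptions. They do not estimate what will happen, and the documents give neither the size nor the direction of any shift. This is a cheap improvement to a secondary analysis and does not threaten the trial's main conclusion.

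**What to change.** 1. Reconcile Screening, Baseline Visit, Visit Windows and Table 1.0 so that PSI-SF and CGSQ-SF are completed at the Characterization/Medical Assessment visit, before the coordinator sends the assignment email. ABC can move with them if convenient.
2. Name these values in the Analytic plan as the baseline covariate for Secondary Outcome #2.
3. Leave PTP and CGI-S at the Baseline Visit. The PTP section has the evaluator draw on caregiver home data, and the Baseline Phase record does not exist at characterization. Keep the Week 4, 8 and 28 windows anchored on the Baseline Visit.
4. For children already assessed on the first treatment day, add a sensitivity comparison of Week 8 PSI and CGSQ scores without baseline adjustment. A baseline shift cannot affect it. It costs precision: at r = 0.6, SE = √(2/46) = 0.209 against 0.167, which is 25% larger.

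**Cost.** No new visits, measures or participants. Table 1.0 allows 5 minutes for PSI and 7 for CGSQ-SF, so about 12 minutes move to an earlier visit; the REDCap section already allows online completion. The baseline falls 2 to 3 weeks earlier, so its correlation with Week 8 may drop slightly. If r fell from 0.6 to 0.5 (assumed), the SE would rise from 0.167 to √(2 × 0.75/46) = 0.181, about 8%. Constipation treatment during the Baseline Phase would fall inside the change score in both arms. The change does not address unblinded reporting at Week 8.
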